**DO NOT DELETE ANY QUESTIONS FROM THIS TEMPLATE**

**PI Name:** [name]

**Study Title:** Development and pilot evaluation of a novel cooking skills intervention to prevent diabetes

**IRB No.:** IRB00018839

**PI Version No. / Date:** V2/ 01/05/2022

**I. Aims of the Study:** *Describe the aims/objectives of the research and/or the project's research questions or hypotheses.*

The Aim of this study is to **test the feasibility, acceptability, and preliminary effectiveness of the DPP Cooks compared with the standard DPP**. We will conduct a randomized pilot trial to test the feasibility and acceptability of DPP Cooks compared with the standard DPP among low-income adults. Data collection will occur at baseline, 4 months, and 12 months. The primary outcome is weight loss. Secondary outcomes include: dietary intake and quality; cooking confidence, attitudes, behaviors, and class attendance. Post intervention, I will also conduct focus groups with two groups: 1) with participants to understand their intervention experiences, and 2) with providers to examine program implementation and satisfaction.

**II. Background and Rationale:** *Explain why this study is being done. Summarize briefly what is already known about the issue and reference previously published research, if relevant.*

Incorporating targeted cooking skills interventions into behavioral weight loss programs to prevent type-2 diabetes, a growing public health problem that disproportionately impacts low-income populations, may be important to facilitate sustained dietary change, weight loss, and reduce risk of developing diabetes. The goal of this proposal is to create, and pilot test in a randomized pilot trial, a new cooking skills intervention to supplement the existing Diabetes Prevention Program while supporting the career development of a new investigator who aspires to a research career focused on preventing diet related diseases. Findings from this study will examine the importance of cooking skills for improving dietary intake, weight loss, and diabetes indicators, and will evaluate potentially important modifications to the DPP.

**III. Study Design:**

A. *Provide a BRIEF overview of your study design and methods. The study design must relate to your stated aims/objectives. DETAILS WILL BE REQUESTED LATER. If your study also involves analysis of existing data, please complete Section XI, "Secondary Data Analysis of Existing Data" in the last part of this research plan. If your study ONLY involves analysis of existing data, please use the research plan template for secondary data analysis (JHSPH IRB Research Plan for Secondary Data Analysis of Existing Data/Specimens).*

This study is a randomized control pilot trial testing the DPP Cooks against standard DPP. DPP is a 12 month diabetes prevention behavioral weight loss program developed by the CDC and implemented

nation wide. Participants meet weekly for the first 6 month in group sessions, then meet less frequently over the last 6 months to help them maintain the behavioral changes (re: diet and physical activity) they made in the first six months. For this trial, up to 48 participants will be randomized 1:1 to participate in the 12 month DPP or the 12 month DPP *plus* an additional 6 cooking skills sessions (DPP Cooks) during the first 4 months of the DPP. The primary outcome, weightloss, is collected at weekly DPP sessions. The secondary outcomes will be collected via online surveys at baseline, 4 months and 12 months, and via the Remote Food Photography Method (RFPM) at baseline and 4 months.

- B. *Provide a sample size and a justification as to how you arrived at that number. If you use screening procedures to arrive at a final sample, distinguish the screening sample size from the enrolled sample size; a table may be helpful. For electronic survey studies involving online recruitment and survey completion: consider how you will set controls on how many people will join your study.*

The target sample size of 48 individuals, randomized 1:1 was based on the fact that this is a pilot feasibility trial so we are not necessarily concerned with detecting statistically significant results. Budget constraints preclude a higher sample size. This sample size will allow us to test the DPP Cooks with several cohorts to understand implementation and prepare for a larger, fully powered study in the future.

- C. *Does your study meet the NIH definition of “clinical trial”: “A research study in which one or more human subjects are prospectively assigned to one or more interventions (which may include placebo or other control) to evaluate the effects of those interventions on health-related biomedical or behavioral outcomes”? If yes, the study must be listed on [clinicaltrials.gov](http://clinicaltrials.gov), study personnel must complete GCP training, and federally funded studies must post consent forms on approved sites, like [clinicaltrials.gov](http://clinicaltrials.gov).*

Yes, this study meets the definition of a clinical trial. The study has been entered in [clinicaltrials.gov](http://clinicaltrials.gov), but has not been published yet. It will be published when the IRB is approved prior to beginning any research activities.

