Eligibility criteria for DPP participation are well established and screening procedures have been in place for years by DPP program staff. These procedures will be followed per usual for this study. DPP staff will determine whether the participant is eligible for the DPP based on medical chart review or based on telephone screening (self-report) per usual protocols and in compliance with CMS standards. DPP eligibility criteria are the following:

- 18 years of older and not pregnant at the time of enrollment
- BMI of 25 or higher **AND**
- HbA1C: 5.7-6.4% **OR** fasting plasma glucose: 100-125mg/dL **OR** 2-hour plasma glucose (after a 75g glucose load): 140-199 mg/dL **OR** previously diagnosed with gestational diabetes, **OR** high-risk result (score of 5 or higher) on the prediabetes risk test

We will create a spreadsheet in which potential participants are all assigned a participant number and where the PII information will be stored. In all other study documents, the participant will be identified by their ID number, not the PII. The spreadsheet linking PII to the participant number will be stored in a separate folder in OneDrive. When a participant is not eligible, or chooses not to enroll in the study, their PII will be deleted immediately.

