#### Community recruitment procedure:

When a potential participant expresses interest in the study, they will contact us (contact information will be provided on recruitment materials). If via study website or social media ad, they will also have the ability to fill out a brief online form that will collect their name, email, and phone number so that we can contact them. Participants who express interest in the study will be screened for eligibility over the phone by study staff. First, we will confirm that they are over 18, are able to attend DPP meetings at the Under Armour house, have a mobile phone (iPhone or Android) that can take photographs, and that they are able to commit to the 12 month study period. We will ensure that they do not meet the other exclusion criteria. We will ensure they fully understand the data collection obligations for the study participation and answer any questions they have. We will refer them to the DPP partner staff (e.g. Brancati Center or University of Maryland) for them to confirm eligibility using their usual procedures (see above). The DPP partner staff will then confirm with us via the OneDrive spreadsheet whether the potential participant is eligible (yes/no) per CDC guidelines to participate in the DPP. They will not share specifics about which eligibility criteria were met. We will then contact the participant to confirm with them that they are eligible for the study and work with them to find an

upcoming study cohort that works for their schedule. We will again go over the study protocol with them and obtain oral informed consent.

DPP referral recruitment procedure:

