**C. Study Implementation:**

1. *Describe the procedures that participants will undergo. If complex, insert a table below to help the reviewer navigate.*

All participants will receive the DPP intervention, a 12 month behavioral weight loss intervention developed by the CDC. The DPP is an evidence-based, standardized curriculum. It requires 1 year of program enrollment divided into two phases. In phase one, participants attend at least 16 1-hour weekly group sessions, and phase 2 includes at least 6 one-hour sessions during the last 6 months.

In the DPP, participants will have weekly group meetings with a trained coach and other participants (usually between 8-12 people in a cohort). Participants receive coaching and social support around topics such as nutrition and physical activity. Participants receive written materials to support their behavior change. They report current weight and minutes of physical activity at every DPP session which is recorded by the coach.

DPP sessions will take place virtually over Zoom.

In the DPP Cooks group, participants will also receive 6 additional 2-hour cooking skills classes throughout the first 4 months of the study period. The cooking classes will be taught by a professional chef-instructor at the *American Heart Association Simple Cooking with Heart Teaching Kitchen* located in the Under Armour House at [name] in Baltimore City. DPP Coaches will also attend the cooking classes. Research Assistants from the study team will also be on hand to assist and to help with clean up.

If the teaching kitchen is not open due to COVID-19 restrictions, cooking classes will also take place virtually over Zoom. The professional chef-instructor has experience leading virtual classes since classes pivoted to virtual in March 2020. If cooking sessions are virtual, we will deliver food and equipment needed for each session to the participant's home or arrange a pick up time for participants to pick up food at the teaching kitchen location (study staff will prepare bags of food for pick up and will be available at pre-arranged time for participants to come pick up). Study staff will not enter the home, but will deliver it to the participant's doorstep and will remain outside (and masked) to ensure it is received.

**We begin this study with virtual DPP Cooks classes. We will not begin in person classes at the teaching kitchen until we have been approved by the IRB to do so.**

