The standard DPP group (control) will be offered a cooking skills session at the completion of the study as well as a participant workbook from the DPP Cooks.

All participants will have the following data collected:

Measure	Method	Baseline	4 months	12 months
Weight loss (kg and % of body weight)	In DPP meetings	X	X	X
Diet quality (3 days at each timepoint)	RFPM	X	X	
Cooking skills/ attitudes/ behaviors	Online Survey	X	X	X
Food Agency	Online Survey	X	X	X
Cooking confidence	Online Survey	X	X	X
Food security status	Online Survey	X	X	X
Demographics	Online Survey	X		
Acceptability of the DPP cooks	Interview			X
DPP session attendance	DPP Coaches			X

- ]
2. *Describe the number and type of study visits and/or contacts between the study team and the participant, how long they will last, and where/how they will take place.*

[ As described above, participants will participate in the DPP, which meets weekly for approximately 1 hour for six months, then approximately monthly for the last 6 months. Participants in the intervention arm (DPP Cooks) will have an additional 6 sessions in a teaching kitchen (2 hours each, 12 hours extra total). If the teaching kitchen is not open due to COVID-19 transmission rates, cooking classes will be held virtually over Zoom. If cooking sessions are virtual, study team staff will deliver the food and equipment needed to participant's homes. Study staff will maintain a safe distance when they deliver and will not enter participant's homes. Staff will drop off food and make sure it is received.

**We begin this study with virtual DPP Cooks classes. We will not begin in person classes at the teaching kitchen until we have been approved by the IRB to do so.**

The DPP Cooks arm will also be sent text messages during the latter 8 months of the intervention (after the 6 cooking sessions are complete) to act as cues to action to keep cooking and using the skills and recipes they developed.

Weight loss data will be collected per usual during DPP sessions by the coach. During virtual DPP, weight has been self-reported by the participant using DPP provided scales. Weight data is reviewed by the DPP team for quality and any issues are resolved with the participant. Weight data is collected in compliance with CMS standards. Weight data will be inputted by DPP staff into a spreadsheet saved on OneDrive. Participants will be identified by their study ID number only.

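### Weight, the primary outcome, is obtained only in DPP sessions, and no route is named for randomized participants who stop attending; mainly the 12-month weight is exposed, with bias of unknown size and direction

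*Combined protocol and SAP*

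**What the plan says.** Section III.A: "The primary outcome, weightloss, is collected at weekly DPP sessions". Section V.C.1 says of participants: "They report current weight and minutes of physical activity at every DPP session which is recorded by the coach". Section V.C.2 repeats it: "Weight loss data will be collected per usual during DPP sessions by the coach". The measures table in V.C.1 gives DPP meetings as the only method for weight, and VI.7 again describes weights reported and recorded in those meetings.

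The measures table is introduced with "All participants will have the following data collected" and marks weight at baseline, 4 and 12 months. The Qualtrics surveys run at the same three time points, outside the sessions, but weight is not listed under them.

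Sessions are weekly for six months, "then approximately monthly for the last 6 months". The nearest text to a follow-up procedure is in V.C.2: "Weight data is reviewed by the DPP team for quality and any issues are resolved with the participant". The same paragraph says that weights in virtual DPP are self-reported from DPP-provided scales and that collection follows CMS standards. It does not mention people who miss sessions or leave.

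The analysis plan (V.C.4) compares change from baseline to 4 and to 12 months between arms. It states no method for missing weights.

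**The concern.** The plan promises a weight for everyone but names a method that reaches only attenders. Whether the primary outcome is observed therefore depends on attendance. Section I lists class attendance as a secondary outcome, so it is itself something the intervention might change. Contact also differs by arm after the cooking sessions end: only DPP Cooks participants receive the text messages described in V.C.2.

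If people who lose less weight are also less likely to attend, the observed 12-month mean is too favourable in each arm, and more so in the arm with lower attendance. With the same relation in both arms, the better-attended arm's benefit is understated. That is conservative if DPP Cooks is better attended and flattering if it is not.

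The trial is a pilot that does not aim at statistical significance. Preliminary effectiveness is still an aim, weight loss is the primary outcome, and the results are meant to prepare a larger trial. A 12-month weight not taken at the time cannot be recovered later.

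**Working it through.** **Reading the text.** III.A, V.C.1 (text and table), V.C.2 and VI.7 all place weight in sessions, and no section names another route. Someone who leaves during the weekly phase may still have several weights before 4 months. At 12 months the value depends on roughly monthly sessions, so 12 months is the main exposure, though not the only one: very early leavers would lack a 4-month weight too.

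**Inputs.** From the documents: 48 participants randomized 1:1, so 24 per arm. There is no attrition, attendance or SD figure and no power calculation to reproduce. Everything else below is assumed.

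**Bias in a comparison of available change scores.** Standardise weight loss Y. A participant attends at 12 months if a latent variable A exceeds a cut-off c, with P(A > c) = p and corr(A, Y) = ρ. With no true effect, the mean of Y among attenders is ρ·m, where m = φ(c)/p. The bias is ρ × (m in the less-attended arm − m in the better-attended arm). The values of m are 0.274 (85%), 0.497 (70%), 0.350 (80%) and 0.644 (60%).

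| Attendance | Bias, ρ = 0.3 | Bias, ρ = 0.5 | Weights left | SE (SD units) | Bias/SE |
|---|---|---|---|---|---|
| 85% vs 70% | 0.067 | 0.111 | 20 vs 17 | √(1/20 + 1/17) = 0.330 | 0.20, 0.34 |
| 80% vs 60% | 0.088 | 0.147 | 19 vs 14 | √(1/19 + 1/14) = 0.352 | 0.25, 0.42 |

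At ρ = 0 the bias is 0. Equal attendance is no guarantee: at 70% in both arms, with ρ = 0.5 in one and 0.3 in the other, the bias is 0.2 × 0.497 = 0.099 SD. At an assumed SD of 3 to 6 kg, the table's range runs from 0.067 × 3 = 0.20 kg to 0.147 × 6 = 0.88 kg.

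**Using the session weights already collected.** Suppose everyone has an early weight loss X with corr(X, Y) = r, and 12-month loss is modelled on X.
- If drop-out depends only on X, the regression of Y on X is the same in attenders and non-attenders, and the residual bias is about 0.00 SD.
- If drop-out depends on Y itself, the slope among attenders is b = r(1 − ρ²k)/(1 − r²ρ²k), with k = m(m − c). The residual in each arm is ρ·m·(1 − r·b). Example: 80% vs 60%, ρ = 0.5, r = 0.6. At 80%, k = 0.417, b = 0.558 and the residual is 0.175 × 0.665 = 0.116. At 60%, k = 0.578, b = 0.542 and the residual is 0.322 × 0.675 = 0.217. The difference is 0.10 SD.
- Over both scenarios and both values of ρ, the residual is about 0.02 to 0.06 SD at r = 0.8 and 0.04 to 0.10 SD at r = 0.6.

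**Reaching non-attenders by survey.** This calculation uses 12-month weights only, without modelling early ones. If half are reached, the residual is 0.02 to 0.04 SD when they are a random half, and 0.04 to 0.08 SD when they are those closest to attending. The second case is the first formula with p replaced by p + 0.5(1 − p). The weights available become 22.2 vs 20.4, or 21.6 vs 19.2 (24 times that proportion), so the SE falls from 0.330 to 0.307 or from 0.352 to 0.314, even if there was no bias.

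**The case against.** Several points on the other side stand.

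- **Existing weights do much of the work.** Participants report weight at every session, with at least 16 sessions in phase 1 and 6 in phase 2. Modelling those weights brings the bias down about as far as a survey item that reaches half of the non-attenders. The analysis change therefore matters as much as the new item. It cannot help very early leavers who have few or no session weights.
- **Usual DPP procedures may already cover missed sessions.** Issues are resolved with the participant and CMS standards apply. A reader might infer that leavers are certainly lost, or certainly followed up. The text supports neither, because those procedures are not reproduced.
- **Retention is not ignored.** Eligibility requires a 12-month commitment, and $60 of the $100 payment follows 12-month data collection.
- **The bias is small against the noise.** Cohorts usually have 8 to 12 members. At an assumed intraclass correlation of 0.05 and cohort size 10, the SE rises by √(1 + 9 × 0.05) = 1.20, so the ratios of 0.20 to 0.42 fall to about 0.17 to 0.35. The template also asks only for a brief analysis plan.

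Two stronger readings should be resisted. A reader might stretch the model to 90% vs 50% attendance, ρ = 0.5 and an SD of 6 kg, which gives 0.301 × 6 = 1.8 kg. That stacks three assumed extremes that nothing in the documents supports. A reader might also infer that a participant who never attends has no possible baseline weight, so that scales must be delivered before arms are disclosed. DPP staff may hold screening data: "DPP staff will determine whether the participant is eligible for the DPP based on medical chart review or based on telephone screening (self-report". The community-stream limit, "They will not share specifics about which eligibility criteria were met", concerns which criteria were met and does not bar obtaining a weight. The gain is marginal, and changing delivery would need the DPP partners' agreement.

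**Conclusion.** The gap is clear on the text: the primary outcome is promised for all participants at three time points, and the only stated method reaches attenders. Whether unreproduced DPP procedures close it cannot be known. Mainly the 12-month weight is exposed.

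Neither the direction nor the size of any bias can be derived. The 0.07 to 0.15 SD range applies to a comparison of available change scores under the assumed attendance rates and correlations, and modelling existing session weights reduces it to between about 0.00 and 0.10 SD. A reader might infer that the plan favours DPP Cooks. The documents do not support that, because they do not say which arm will attend better or whether attendance relates to weight loss. Attendance is recorded, so a difference between arms would be visible, but recording it does not supply the missing weights. This is a cheap improvement worth making, not a flaw that invalidates the pilot.

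**What to change.** 1. Add one item to the existing 4- and 12-month Qualtrics surveys, sent to every randomized participant whatever their attendance: current weight on the DPP-provided scale, with a phone photo of the display. Add it to the baseline survey where the scale is already in hand, without requiring changed scale delivery.
2. Send text reminders, as already planned for the food photographs, and count the item in the data collection that triggers the existing payments.
3. State in V.C.4 that all session and survey weights enter at their own dates, by assigned arm, in one repeated-measures model.
4. Report the number of weights obtained by arm and time point.
5. If usual DPP procedures already cover missed sessions, say so.

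The cost is one survey item, a sentence or two of analysis plan and a short amendment. Camera phones are already an inclusion criterion. The downsides are slight participant burden, weights that are still self-taken, and survey non-response among leavers that leaves some bias. The documents give no response rate from which to predict how much.

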Diet quality will be collected by the participant by taking photographs of all the food they eat over a 3-day period and uploading those photographs to the SmartIntake app. Participants will be reminded to do this based on text messages from the study team, and the study team will be on hand to assist participants if they run into any problems or need help. Participants will be given a reference card to include in food photographs (e.g. a blank white card with some lines on it to help gauge portion size as well as a paper food tracker and guidebook). Other measures of interest will be collected using online surveys (Qualtrics) at baseline, 4 months and 12 months. Finally, we will invite participants to share their thoughts and experiences with the DPP Cooks intervention in in-depth interviews (over Zoom or phone) at the end of the study (12 months).

]

- [ ]
3. *Describe the expected duration of the study from the perspective of the individual participant and duration overall.*

[The duration of the study is 12 months from start to finish. From the participant's perspective they will attend DPP sessions and some participants will have 6 extra cooking classes. Data collection will not require in person study visits. The participant will have a training session with study team staff to help them install and learn how to use the RFPM app and record their data. This session will take place over zoom before baseline data collection begins.

]

4. *Provide a brief data analysis plan and a description of variables to be derived.*

[The key independent variable for all analyses is an indicator of whether or not the participant is in the control (standard DPP) group or the intervention (DPP Cooks) group. The other key variable is an indicator of time (baseline, 4 months, or 12 months). The primary outcome variables are weight loss (in kg lost, and in % of body weight lost). The secondary outcome variable is dietary intake/quality. We will use the data from the RFPM to calculate Healthy Eating Index-2015 scores. We will also be able to measure fruit and vegetable, as well as carbohydrate intake. Additional secondary outcomes from survey measures will include cooking confidence, cooking attitudes, cooking behaviors, cooking skills, food agency, and food security status. For most analyses we will compare changes in scores from baseline to 4 months and baseline to 12 months between intervention and control groups.]

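### Weight is recorded at every DPP session, but the analysis plan uses only baseline, 4 and 12 months, leaves the other session weights without a planned use, and gives no rule for a missing weight

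*Combined protocol and SAP*

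**What the plan says.** **Collection.** Section III.A states "The primary outcome, weightloss, is collected at weekly DPP sessions". V.C.1 says of participants: "They report current weight and minutes of physical activity at every DPP session which is recorded by the coach". V.C.2 adds that DPP staff enter the weights in a study spreadsheet, and that while the DPP is virtual the weights are self-reported from scales the programme provides.

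**Number of sessions.** V.C.1 gives a minimum: "participants attend at least 16 1-hour weekly group sessions, and phase 2 includes at least 6 one-hour sessions during the last 6 months". V.C.2 describes a fuller schedule: the DPP "meets weekly for approximately 1 hour for six months, then approximately monthly for the last 6 months".

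**Analysis.** V.C.4 states "The primary outcome variables are weight loss (in kg lost, and in % of body weight lost" (closing bracket omitted) and defines time with three levels: "The other key variable is an indicator of time (baseline, 4 months, or 12 months". The comparison is "For most analyses we will compare changes in scores from baseline to 4 months and baseline to 12 months between intervention and control groups". The measurement table in V.C.1 marks weight at the same three points, with DPP meetings as the method.

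**Not stated.** The document does not say which session supplies the 4- or 12-month weight, whether there is a window around the target date, or what is done when a weight is missing. It describes no analysis of the remaining session weights.

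**The concern.** The primary outcome is measured many times per person, but the stated analysis refers to three of those measurements. A change score needs a baseline weight and a weight at the target time, and the described source of weights is the session itself. With no rule for an absent participant, the choice is left until the data are in hand. One possible outcome is a comparison among those who attended a particular session.

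Two things are at stake. The first is precision: budget caps the trial at 48 people (III.B), so using weights already recorded is one of the few ways to narrow the interval. The second is selection: attendance may differ by arm and with weight progress, and class attendance is itself listed as a secondary outcome (section I). The aim includes preliminary effectiveness, and the trial is meant to prepare a larger one, so the estimated difference and its spread will be used.

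**Working it through.** **1. Share of weights with a planned use.** Inputs are from V.C.1, V.C.2 and V.C.4.

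- Minimum schedule: 16 + 6 = 22 sessions. 3/22 = 13.6% used, 19/22 = 86% not.
- Fuller schedule: about 26 weekly + 6 monthly = 32. 3/32 = 9.4% used, 29/32 = 91% not.

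This counts measurements. It does not measure information lost (step 3).

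**2. People with a weight at a time point.** The document gives no attendance figure, so attendance *a* per session is an assumption, taken as independent between sessions. N = 48, 24 per arm (III.B).

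- One session, complete cases: 48*a*. At 50%, 24; at 80%, 38.4.
- Any weight from a three-session window: 48(1 − (1 − *a*)³). At 50%, 48 × 0.875 = 42; at 80%, 48 × 0.992 = 47.6.

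Someone who has left the programme misses every session in the window, so the window figures are optimistic.

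**3. Precision, analytic.** Assumptions: 24 per arm, sessions missed completely at random, change following a random walk with SD 6 kg at 12 months, weighing-error SD 0.5 kg, known covariance, a free mean at each session, the 22-session schedule. Entries are the variance of the 12-month arm mean relative to complete data. The SE reduction is 1 − √(ratio of the two variances).

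| Attendance | Complete case (1/*a*) | Three-time-point mixed model | All session weights | SE reduction vs complete case | SE reduction vs three-point model |
|---|---|---|---|---|---|
| 60% | 1.667 | 1.601 | 1.105 | 18.6% | 16.9% |
| 70% | 1.429 | 1.359 | 1.054 | 14.1% | 11.9% |
| 80% | 1.250 | 1.206 | 1.028 | 9.3% | 7.7% |
| 90% | 1.111 | 1.088 | 1.011 | 4.6% | 3.6% |
| 100% | 1.000 | 1.000 | 1.000 | 0% | 0% |

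Example at 60%: 1 − √(1.105/1.667) = 1 − 0.814 = 18.6%. The 4-month figures are similar: 1 − √(1.068/1.667) = 20.0% at 60% attendance, and 1 − √(1.022/1.250) = 9.6% at 80%.

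A second calculation of the same kind used other assumed SDs (between-person 4.5 kg at 6 months, maintenance 2.5 kg, within-person 0.8 kg) and attendance of 50-80%. At both time points the SE was about 10-27% below complete-case change and about 4-20% below a three-time-point mixed model, with no gain at full attendance.

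**4. Precision, simulated.** With the second set of SDs, 250 trials per attendance level (50/65/80%) and the covariance estimated from the data, the SE of the arm difference was:

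- 4 months: 1.38/1.23/0.99 kg from one session, 0.85/0.87/0.81 kg from the mixed model. At 50%, 1 − 0.85/1.38 = 38%; at 80%, 1 − 0.81/0.99 = 18%.
- 12 months: 2.19/1.95/1.63 kg against 1.55/1.49/1.40 kg, or 29% to 14% smaller.
- Nearest weight within ±2 weeks at 4 months and ±6 weeks at 12 months, without the mixed model: 15-31% smaller at 4 months and 10-17% at 12 months.

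The model was given the correct curve shape, so these gains, and the 38% in particular, are at the favourable end. None of these calculations includes permanent dropout or clustering by DPP cohort.

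**The case against.** A reader might infer that the plan drops anyone who misses one session. The document does not say so. The measurement table names months, not numbered sessions, and V.C.4 is a brief plan that speaks of most analyses. Taking the nearest recorded weight, or fitting a three-time-point model, would fit the text equally well. A weight might also be obtained from an absentee: V.C.2 describes self-report from home scales and follow-up of data problems with the participant, and IX.B ties payment to completing the 4- and 12-month data collection. This objection stands. The finding is that the rule is absent, so such a loss is possible but not planned.

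A reader might also take 86-91% of weights unused as that share of the information thrown away. That does not follow. The weights stay in the spreadsheet, and with full attendance and a free mean at each session the extra weights add nothing to the contrast (last row of the table). Their value lies in standing in for missed sessions and describing the trajectory.

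It is fair to add that a window recovers much of the 4-month loss, and that this is a pilot which disclaims interest in significance (III.B). The window helps less at 12 months, where sessions are about monthly. The pilot argument does not remove the point, because weight loss is the named primary outcome and the estimate is meant to inform a larger trial.

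**Conclusion.** The point holds in limited form. Weights are collected at 22 to about 32 sessions, the stated analysis uses three, and no rule fixes the 4- and 12-month weights or handles a missing one. A model on all session weights is a better method than the stated change scores and needs no new data.

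The gain is conditional. At assumed attendance of 50-80% it is roughly 10-30% off the SE relative to complete-case change, less relative to a three-time-point mixed model, and nothing at full attendance. It rests on assumed SDs and independent attendance, and it ignores permanent dropout and clustering.

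It would be too strong to say that the model removes the bias from attendance. It still uses only reported weights and relies on missing at random, so it reduces the bias from informative dropout without eliminating it.

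**What to change.** In V.C.4, replace the two change-score comparisons for weight with one linear mixed model:

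- all session weights from all randomized participants, in their assigned arm;
- baseline weight as covariate;
- a prespecified time shape, for example piecewise slopes or a spline, that may differ by arm;
- correlation within person, and a term for DPP cohort. Each cohort sits wholly within one arm (V.C.5.A), so this should be a random effect; a fixed effect for every cohort would absorb the arm difference. At the usual 8-12 people per cohort, 48 people make about 4-6 cohorts (48/12 to 48/8), so the cohort variance will be poorly estimated;
- arm differences read off at 4 and 12 months.

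As a prespecified sensitivity analysis, use the recorded weight nearest each target date within a stated window (for example ±2 weeks at 4 months and ±6 weeks at 12 months), with a rule for ties. Note that the 12-month window is largely one-sided and holds only one or two roughly monthly sessions. State the missing-data assumption.

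The cost is slightly more analysis work, dependence on the chosen time shape, and the missing-at-random assumption. No new data, visits or staff are needed.
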